5.5 Outcomes

5.5.1 Primary Outcomes

The primary outcome is defined as any of the below occurring during the 9 weeks following administration, at least possibly related to the ATIMP, not surgery alone:

- Reduction in visual acuity by 15 ETDRS letters or more
- Severe unresponsive inflammation

- Infective endophthalmitis)
- Ocular malignancy
- Grade III or above non-ocular SUSAR. (See Section 5.11.3)

5.5.2 Secondary Outcomes

The secondary outcomes are measures of the efficacy of the ATIMP; these will be performed on an individual participant basis and will be descriptive in nature. Secondary outcomes are:

- Any improvements in visual function from baseline that are greater than the test-retest variation and are sustained for at least two consecutive assessments.
- Any improvement in retinal function from pre-intervention that is greater than the test-retest variation and measurable by electroretinography (ERG).

If no ERG is previously detectable, then the presence of any reproducible response with appropriate waveform would be significant. If an ERG is there to start with, any of the following would be significant: an improvement in amplitude of >50 % in DA 0.01 b-wave (rod system sensitivity); bright flash DA 10 a-wave (photoreceptor improvement); the 30Hz flicker; and the LA 3.0 photopic a- and b-waves. In terms of timing: > 3ms improvement in photopic parameters and bright flash DA 10 a-wave; 3-6ms for the DA 0.01 and DA 10.0 b-waves.

- Quality of life will be measured by the Impact of Visual Impairment (IVI) questionnaire and the EQ5D- 5Land EQ-5D-Y

5.6 Trial Assessments

Table 2: Trial assessments

	Screening	Baseline			ATIMP admin	D1	D3	W1	W2	W4	W6	W9	W12	W24
Flexibility of schedule (\pm days)		- 3 months			Day 0	\pm 0D	\pm 1D	\pm 2D	\pm 4D	\pm 7D	\pm 7D	\pm 7D	\pm 14D	\pm 14D
Visit number	1	2	3	4	5	6	7	8	9	10	11	12	13	14
Informed consent	•													
Physical exam	•													
Medical history	•							•	•	•	•	•	•	•
Eligibility determination	•													
IMP administration					★									
Adverse event review		•	•	•	•	•	•	•	•	•	•	•	•	•
Concomitant medication review	•	•	•	•	•	•	•	•	•	•	•	•	•	•
Genetic screening	•													
Pregnancy test	•				•									
Vital signs (including height and weight) ⁵	•	•				•		•	•	•				
Haematology/Renal Function		•				•		•	•	•	•			
Biochemistry/glucose		•				•		•	•	•	•			
Serology		•								•			•	•
PCR						•				•				
QoL questionnaires (IVI and EQ5D-5L)		•												•
Visual acuity ⁶	•	•	•	•		•	•	•	•	•	•	•	•	•
Contrast sensitivity	•	•	•	•									•	•
Reading speed		•	•	•									•	•
Colour vision		•	•	•									•	•
Octopus perimetry		•	•	•									•	•
Full field Stimulus Testing ⁷		•	•	•									•	•
Microperimetry (mesopic and scotopic)		•	•	•							•		•	•

5.6.1 Early Stopping of Follow-up

If a participant chooses to withdraw from the trial, they should continue to be followed up as closely as possible to the follow-up schedule defined in the protocol, providing they are willing. If, however, the participant exercises the view that they no longer wish to be followed up either, this view must be respected. Data already collected will be kept and included in analyses according to the intention-to-treat principle for all participants who stop follow up early.

Participants who stop trial follow-up early may be replaced.

5.6.2 Loss to Follow-up

This is a highly motivated patient group who are likely to remain committed to the research. Continued follow up of all participants will be strongly encouraged whilst being mindful of the importance of ensuring the autonomy of participants in regards to their treatment decisions and willingness to continue to participate in the trial.

5.6.3 Trial Closure

The end of the entire trial is considered the last follow-up visit of the last participant. For each participant, the trial will terminate at the last scheduled visit 6 months following ATIMP administration. The MHRA will be notified of the end of the trial within 90 days of its completion.

5.6.4 Passive/Long Term Follow-Up After the End of the Trial

At the end of this trial, participants will be invited to enrol in a 5-year follow-up study to determine longer term safety and efficacy.

5.7 Sample Size

This is a Phase I/II trial to establish safety and assess indicators of potential efficacy of the ATIMP, therefore there is no formal sample size calculation. The trial will enrol up to 27 participants (up to 18 in the dose escalation phase and a further 9 in the confirmatory phase), as described in section 4.3.2.2. The limited number of participants is necessitated by the rare nature of the disease under investigation. We estimate that inclusion of up to 27 participants will be sufficient to determine the safety and tolerability of the intervention.

5.8 Recruitment and Retention

5.8.1 Recruitment

Most participants will be recruited through Moorfields Eye Hospital or the Kellogg Eye Center, or on referral by ophthalmologists within or outside the UK or the US. Members of their direct clinical care team will approach potential participants in the first instance to discuss whether they would like to consider participating. Alternatively, potential participants may contact the trial team independently.

We expect to recruit up to 27 participants within a period of 36 months.

5.8.2 Retention

Participants will be supported to remain in follow-up by regular contact as per the protocol, provision of a 24-hour hotline to a member of the trial team

5.9 Assignment of Intervention

5.9.1 Allocation

All participants will receive the same intervention in this open label, non-randomised trial: subretinal administration of AAV2/5-OPTIRPE65. The dose received by each participant will depend on the time/order of their enrolment in the trial, and the extent to which dose-limiting events observed in earlier participants during the dose-escalation phase (See Sections 4.3.2 and 5.4.4 for dose escalation information). Children will not be enrolled in the trial until the safety profile and recommended dose have been established in adults.

5.10 Data Collection, Management and Analysis

5.10.1 Data Collection, Management and Entry

Syne qua non will be responsible for data management activities for the study.

Data will be captured in a fully validated, 21 CFR Part 11 compliant Electronic Data Capture (EDC) system provided by Syne qua non.

Syne qua non will grant authorised site staff with access to the EDC system following system training and a successful competency assessment.

Data required by the protocol will first be recorded on source documents (e.g. medical records and study-specific data capture tools as needed) and then entered by site staff into the EDC system. All information in EDC must be traceable to these source documents. Any data recorded directly into EDC will be defined prior to the start of data collection. All data is currently anticipated to be associated with source data records.

Data validation checks will be activated during data entry to identify data discrepancies. Appropriate error messages will be displayed to allow modification or verification of data by the site staff.

Monitoring staff will review the data for completeness and accuracy, instructing site staff to make any required corrections or additions via data queries. Syne qua non will run further automated validation checks and review the data, raising further data queries to the sites for resolution of any inconsistencies.

The Investigator will review the eCRFs for completeness and accuracy then electronically approve the data, retaining full responsibility for its accuracy and authenticity.

Medical history and adverse events will be coded using the Medical Dictionary for Regulatory Activities (MedDRA) terminology. Prior and concomitant medication will be coded using the World Health Organization Drug (WHO)-Drug Dictionary which employs the Anatomical Therapeutic Chemical (ATC)

classification system. Further coding details and data management processes will be described in a Data Management Plan (DMP).

All actions within the EDC system are captured within an audit trail. After all data have been entered, validated and signed off, the database will be locked.

At the end of the study, PDF copies of the eCRFs for each subject and supporting information will be provided to sites and the Sponsor. The electronic data will be provided to the Sponsor.

5.10.3 Non-Adherence and Non-Retention

Participants who withdraw from the trial after the intervention will be encouraged to participate in any of the planned follow-up scheduled for the trial with their consent, and data from these subjects collected prior to withdrawal may be included in the interpretation of results.

Reasons for withdrawal from the trial will be documented on a withdrawal CRF where possible, in addition to the procedures and CRF for the final visit (6 month) assessments with the participant's consent.

5.10.4 Statistical Methods

5.10.4.1 Statistical Analysis Plan

A formal statistical analysis plan will be written by the trial sponsor and approved by the IDMC. This trial is an open label, no crossover, Phase I/II trial involving a small number of participants, and analysis of the primary and secondary outcomes will be descriptive in nature.

5.10.4.2 Statistical Methods – Primary Outcome Analysis

The primary outcome is safety of subretinal administration of the ATIMP, defined as any of the below occurring during the 9 weeks following administration, at least possibly related to the ATIMP, not surgery alone:

- Reduction in visual acuity by 15 ETDRS letters or more
- Severe unresponsive inflammation
- Infective endophthalmitis
- Ocular malignancy
- Grade III or above non-ocular SUSAR (See Section 5.11).

The number of DLEs at each dose level will be summarised by cohort and overall.

It is anticipated that the vector will be administered at the MTD in up to 15 participants (6 adults in the dose escalation phase and up to 9 further adults and children in the confirmatory safety phase). Safety data relating to these participants will allow estimation of an upper bound for the true event rate through a 95% confidence interval.

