4.3.2.1 Dose escalation criteria and Dose Limiting Events

Dose escalation will be undertaken in adults, based on an escalation rule around Dose-Limiting Events (DLEs). An IDMC will review data from a minimum of 9 weeks of follow up from each cohort of 3 participants, before recommending the next dose to be assessed in a further cohort of participants.

A DLE is defined as any of the below occurring during the 9 weeks following administration, at least possibly related to the ATIMP, not surgery alone:

- Reduction in visual acuity by 15 ETDRS letters or more
- Severe unresponsive inflammation
- Infective endophthalmitis
- Ocular malignancy or
- Grade III or above non-ocular SUSAR (see section 5.11.3)

Severe unresponsive inflammation will be defined according to the Standardisation of Uveitis Nomenclature (SUN) Working Group grading system (Jabs *et Al.* 2005) i.e.

- anterior chamber cells 3+ (26-50 cells in a field size of 1mm x 1-mm slit-beam), or
- anterior chamber flare 3+ (marked, iris and lens details hazy), or
- vitreous haze 3+ (Ophthalmology 1985; 92:467-71)

that fails to improve by 2 steps (or to grade 0) during a 9-week period.

Review of safety data will be undertaken by the IDMC prior to each dose escalation. Children will be included at up to the highest safe vector dose recommended by the IDMC, once a safety profile has been established in adult participants.

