4.3.2.2.4 Additional considerations

In the event of a DLE in one of the 3 participants at any given dose, the cohort will be expanded at the same dose level. The IDMC will review the safety data and confirm that additional participants may be treated at this dose. The IDMC may recommend that the same dose of ATIMP is administered to additional participants. The dose escalation will continue until 3 participants have been either administered the highest dose without any DLEs, or until at least 2 participants among a cohort of 3 to 6 participants experience DLEs (i.e., $\geq 33\%$ of participants with a DLE at that dose level), in which case the recommended dose will be the level below this toxic dose. In the event that 1 or 2 DLEs are seen at the first dose level, the IDMC may recommend administering a lower dose to that described in the protocol to a cohort of participants.

Table 1: Dose escalation table

Number of DLEs		Action	Details
Low dose			
Participants 1-3	Participants 4-6		
0/3		Increase	Give intermediate dose to next cohort of participants
1/3		Remain	Give low dose to another cohort of participants (Pt 4-6)
≥ 2/3		Stop	MTD not found. Consider lower dose
	≤ 1/6	Increase/stop	Has higher dose been tried? No: Give intermediate dose to next cohort of participants Yes: MTD found – low dose
	≥ 2/6	Stop	MTD not found. Consider lower dose
Intermediate dose			
Participants 1-3	Participants 4-6	Action	Details
0/3		Increase	Give high dose to next cohort of participants
1/3		Remain	Give intermediate dose to participants 4-6
≥ 2/3		Decrease/stop	Give low dose to 3 more participants. If 6 participants already had low dose, stop. MTD found – low dose.
	≤ 1/6	Increase/stop	Has higher dose been tried? No: Give high dose to participants 1-3 Yes: MTD found – intermediate dose
	≥ 2/6	Decrease/stop	Give low dose to participants 4-6. If 6 participants already had low dose, stop. MTD found – low dose
High dose			
Participants 1-3	Participants 4-6	Action	Details
0/3		Remain	MTD found – give high dose to participants in confirmation phase
1/3		Remain	Give high dose to participants 4-6
≥ 2/3		Decrease/stop	Give intermediate dose to participants 4-6. If 6 participants already had intermediate dose, stop. MTD found – intermediate dose
	1/6	Stop	MTD found – high dose
	≥ 2/6	Decrease/Stop	Give intermediate dose to participants 4-6. If 6 participants already had intermediate dose, stop. MTD found – intermediate dose

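### The 95% bound at the MTD includes the adults whose results chose the dose, so the pooled rate is biased low and the 95% level is not guaranteed at higher true rates

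*Combined protocol and SAP*

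**What the plan says.** Section 5.10.4.2 expects a pool at the MTD: "It is anticipated that the vector will be administered at the MTD in up to 15 participants", made up of "6 adults in the dose escalation phase and up to 9 further adults and children in the confirmatory safety phase". The only interval promised for the primary outcome rests on that pool: "Safety data relating to these participants will allow estimation of an upper bound for the true event rate through a 95% confidence interval." Neither the interval method nor its sidedness is given. Section 5.10.4.2 also summarises DLE counts by cohort and overall, and 5.10.4.1 calls the analysis descriptive and defers detail to a formal SAP.

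Selection and estimation use the same event. Section 4.3.2.1 begins its definition: "A DLE is defined as any of the below occurring during the 9 weeks following administration". The primary outcome in 5.10.4.2 is "defined as any of the below occurring during the 9 weeks following administration, at least possibly related to the ATIMP, not surgery alone". Both list the same five events.

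Section 4.3.2.2.4 continues escalation until the top dose is cleared or "until at least 2 participants among a cohort of 3 to 6 participants experience DLEs". In Table 1, 0/3 at the high dose ends the search: "MTD found – give high dose to participants in confirmation phase". The pool is then 3 + 9 = 12 rather than 15.

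**The concern.** An ordinary binomial interval assumes that the number of events was free to take any value. For the escalation adults at the MTD it was not. Had two or more of them had a DLE, the dose would not be the MTD and their data would not be in the pool. Their count is capped at 0 or 1 by the rule that admitted the dose, so the pooled total is not binomial. The confirmatory participants played no part in choosing the dose.

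This bound is the only inferential statement about the primary outcome, and it concerns the dose that caps what children may receive (4.3.1, 4.3.2.2.5). A reader should know how much of its apparent precision comes from data that had to look good.

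**Working it through.** **Inputs.** The 3+3 rule and MTD definitions come from Table 1. The pool is 6 + 9 (5.10.4.2), or 3 + 9 after 0/3 at the high dose. The 95% level is from 5.10.4.2. Assumptions: an exact (Clopper-Pearson) interval, two-sided, so the upper tail is 2.5%; all 9 confirmatory participants treated at the MTD; true DLE rate p unknown and shown over a range, with q = 1 − p.

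**The plan's own figure.** 6 + 9 = 15, as stated. The plan gives no numerical bound to reproduce.

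**Two cases under strict Table 1.**
- *High dose.* Accepted after 0/3 with probability q³ (pool 12), or after 1/3 then 0/3 with probability 3pq²·q³ (pool 15). This is the 3 + 9 case, with a 1/6 branch.
- *Six adults at the MTD*, as 5.10.4.2 anticipates. Accepted at 0 or 1 of 6, with probability q⁶ + 6pq⁵ (pool 15). Table 1 also gives this case for a lower dose settled on after de-escalation.

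**Bias, at p = 20%.**
- Six adults: q⁶ = 0.262 and 6pq⁵ = 0.393, sum 0.655. Mean events among the six, given acceptance, = 0.393/0.655 = 0.60, against 1.20 without selection. Expected pooled rate = (0.60 + 9 × 0.20)/15 = 16.0%.
- High dose: q³ = 0.512 and 3pq⁵ = 0.197, giving weights 0.722 and 0.278. Expected pooled rate = 0.722 × 1.8/12 + 0.278 × 2.8/15 = 16.0%.

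| True rate | Expected pooled rate, high dose | Expected pooled rate, six adults |
|---|---|---|
| 10% | 8.5% | 8.7% |
| 20% | 16.0% | 16.0% |
| 30% | 23.2% | 22.8% |

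Enumerating the whole three-dose design over 556 sets of non-decreasing dose rates (2% to 50%, chance of selecting an MTD at least 0.2) gave a downward bias in every one.

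**Coverage.** The zero-event upper limit is 1 − 0.025^(1/n): 26.5% for n = 12 and 21.8% for n = 15. The bound cannot fall below a true rate smaller than that limit, so the chance of a miss there is 0%. Above it:
- *High dose, p = 26.5%.* A miss requires 0/12. The chance of the 0/3 branch, given acceptance, is 0.397/0.568 = 0.70. The chance of 0/9 is 0.735⁹ = 0.063. The product is 4.4%.
- *Six adults, p = 32%.* The limit for 1/15 is 31.9%, so a miss means 0 or 1 event in 15. Without selection that has probability 2.48%. Every such outcome lies among the accepted ones, and acceptance has probability 0.378, so the conditional miss rate is 0.0248/0.378 = 6.6%.
- *The excess comes and goes.* With six adults the miss rate is 4.0% at 22%, 2.5% at 25%, 1.1% at 30%, 6.6% at 32% and 4.4% at 35%.
- *Averaged over whichever dose is selected.* The miss rate is 0% for true rates of 5/10/20% at the three doses, 1.0% for 10/20/30% and 1.2% for 20/30/40%. It exceeded 2.5% in 119 of the 556 sets, at worst 6.5%.
- *Read as a one-sided 95% bound (nominal 5%).* With six adults the miss rate is 5.4% at 20% and 10.7% at 28%.

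**Can the rule accept such doses?** At p = 30%, acceptance at the dose itself has probability 0.343 + 0.151 = 0.49 (high dose) or 0.42 (six adults).

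**Confirmatory participants alone.** The count is binomial, so the miss rate never exceeds 2.5%. The limit for 0/9 is 1 − 0.025^(1/9) = 33.6%.

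**The case against.** The strongest reply is that the coverage problem is narrow. An exact interval is conservative in small samples, and at true rates up to about 22% or 26% that conservatism more than absorbs the selection effect. The rates quoted above sit just past jumps in a sawtooth. This stands. A reader might infer that the bound generally misses more often than 5% or 2.5% of the time; the enumeration does not show that.

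Second, dropping the escalation adults costs accuracy. Root mean squared error for nine confirmatory participants is 13.3 points at a true 20% and 15.3 at 30%, against 10.4 and 12.8 for the pool at the high dose. This also stands, and is a reason to show both figures rather than replace one with the other.

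Third, the analysis is descriptive and counts are given by cohort. That lets a careful reader separate the stages, but the only interval promised is the pooled one, and it is said to bound the true rate.

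Two stronger readings are tempting. One is that the bound leads to an unsafe dose in children. Nothing in the plan makes a dosing decision depend on it: dose choice rests on DLE counts and IDMC agreement. The other concerns 5.7, which says: "We estimate that inclusion of up to 27 participants will be sufficient to determine the safety and tolerability of the intervention." One might want to replace that with zero-event limits of 12.8% for 0/27 and 21.8% for 0/15. Strict Table 1 does not allow 0/27, because a cohort grows from 3 to 6 only after a DLE at that dose or a higher one. It does not allow 0/15 at the high dose either, because six adults there means one already had a DLE. Those figures should not be used.

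**Conclusion.** The point holds in this form: pooling makes the estimated DLE rate at the MTD too low whenever Table 1 is followed. The shortfall is small if the true rate is low (about 1 to 1.5 points at 10%) and material if it is not (4 points at 20%, 7 at 30%). The 95% level is not guaranteed after selection; it can fail once the true rate passes about 22% (6 + 9) or 26% (3 + 9), and only at some rates beyond that.

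These sizes assume strict Table 1, an exact two-sided interval and nine confirmatory participants at the MTD. The IDMC may add participants at its discretion (4.3.1, 4.3.2.2.4), the expansion cohort may be treated below the agreed highest dose (4.3.2.2.5), and the interval method is unstated, so the exact figures would shift. The confirmatory-only result is free of selection provided that confirmatory DLEs do not themselves change the dose or halt enrolment at it, and it mixes adults with children. This is worth correcting as a cheap improvement to reporting; it is not a flaw in the conduct of escalation.

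**What to change.** In 5.10.4.2, and in the formal SAP that 5.10.4.1 promises:

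1. Report the DLE proportion with an exact (Clopper-Pearson) 95% interval, sidedness stated, for the confirmatory participants treated at the MTD alone. Use the actual number, which may be below 9.
2. Show the pooled figure beside it, labelled as including the data used to select the dose and therefore biased low.
3. State that the escalation part of the pool may be three adults rather than six.

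If 5.7 is reworded at the same time, quote only limits that can occur, such as 33.6% for 0/9, or 26.5% for a pooled 0/12 at the high dose with its label.

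The change is to wording and tables; no dose, visit or participant number changes. The cost is a wider and more variable headline interval, 33.6% instead of 26.5% at the high dose with no events, and wider still if fewer than nine are treated at the MTD.

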5.10.4.3 Statistical Methods - Secondary Outcome Analysis

The secondary outcomes are measures of the efficacy of the ATIMP; these will be performed on an individual participant basis and will be primarily descriptive in nature. Standard assessments will be used to measure visual function and established methods of analysis, appropriate for the assessment will be used to evaluate the data. For specialist assessments, data will be analysed by the expert team member(s) who developed the assessment. Final data will be reported descriptively.

Efficacy will be indicated by:

- 1) Any improvement in visual function from baseline that is greater than the test-retest variation for that test and is sustained for at least two consecutive assessments.
- 2) Any improvement in retinal function from pre-intervention assessment that is greater than the test-retest variation and measurable by electroretinography (ERG)

If no ERG was previously detectable, then the presence of any reproducible response with appropriate waveform would be clinically significant. If an ERG was there to start with, any of the following would be significant:

- an improvement in amplitude of >50 % in DA 0.01 b-wave (rod system sensitivity);
- bright flash DA 10 a- wave (photoreceptor improvement);
- the 30Hz flicker; and
- the LA 3.0 photopic a- and b-waves.

In terms of timing: > 3ms improvement in photopic parameters and bright flash DA 10 a-wave; 6ms for the DA 0.01 and DA 10.0 b-waves.

Measures will be reported individually and aggregated across participants as the proportion who satisfy the above criteria.

Quality of life patient reported outcome measures will be used to correlate a participant's feeling about their own wellbeing with clinical observations.

Any deviations from the original statistical plan will be approved by the CMT and IDMC and described in the final report, as appropriate.

